#### **PICO:**

Population [P]: patients with oral mucositis attending the National Cancer Institute clinic

Intervention [I]: MEBO

Comparison [C]: Benzydamine Hydrochloride spray

Outcome [o]: clinical improvement and quality of life

Outcome measure		Method of measurement	Unit of measurement
1 ry Outcome	Clinical improvement	World Health Organization (WHO)scale.(1)  Oral Mucositis Assessment Scale (OMAS).(2)	Ordinal
2 ry Outcome	quality of life	Patient-Reported Oral Mucositis( PROMS scale).(3)	Continuous outcome (Score codes).

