#### **10. Eligibility criteria:**

##### **A- Inclusion criteria:**

- 1) Patients having clinical signs of chemotherapy-induced or radiotherapy-induced OM (WHO oral mucositis grading scale: Grade II, III and IV)
- 2) Patients over the age of 18 years
- 3) Patients having no history of allergy, allergic rhinitis and asthma

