### ***Clinical parameters:***

#### **Clinical improvement of the lesion:**

The clinical data will be scored according to The World Health Organization (WHO)scale(1). It is graded from 0 to 4. If the patient has no signs and symptoms, it is graded as 0. If the patient has painless ulcers, edema, or mild soreness, it is graded as 1. If there is painful erythema, edema, or ulcers but able to eat, it is graded as 2. If there is painful erythema, edema, or ulcers but unable eat, it is graded as 3. If there a requirement for parenteral or enteral support, it is graded as 4

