#### **Quality of life**

The secondary outcomes will be quality of life assessed by PROMS scale.(2)

The PROMS scale consists of 10, 100-mm horizontal visual analogue scales addressing oral functions affected by oral mucositis. Participants will be asked to mark a point on the line that best represents their present intra-oral condition. During the baseline examination and prior to their completion of the actual PROMS scale questionnaire, participants were subjected to a few training test-visual analogue scale questions focused on simple everyday topics to familiarize them with the concept of visual analogue scale assisted measurements(19). The participants will

complete the PROMS questionnaire thrice; baseline, after the first week, and at the end of the study after the second week.

1. Mouth pain (Mouth encompass also lips, cheeks, tongue, gums, palate and throat)	
no pain	worst possible pain
_____	
2. Difficulty speaking because of mouth* sores	
no trouble	impossible to speak
speaking	
_____	
3. Restriction of speech because of mouth* sores	
no restriction	complete restriction of speech
of speech	
_____	
4. Difficulty eating hard foods (hard bread, potato chips etc) because of mouth* sores	
no trouble	impossible to eat hard foods
eating hard foods	
_____	
5. Difficulty eating soft foods (Jello, pudding etc) because of mouth* sores	
no trouble	impossible to eat soft foods
eating soft foods	
_____	
6. Restriction of eating because of mouth* sores	
no restriction	complete restriction of eating
eating	
_____	
7. Difficulty drinking because of mouth* sores	
no trouble	impossible to drink
drinking	
_____	
8. Restriction of drinking because of mouth* sores	
no restriction	complete restriction of drinking
drinking	
_____	
9. Difficulty swallowing because of mouth* sores	
not difficult to	impossible to swallow
swallow	
_____	
10. Change in taste	
no change in	complete change in taste
taste	

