## **20. Statistical methods:**

Data will be analyzed using IBM SPSS advanced statistics (Statistical Package for Social Sciences), version 21 (SPSS Inc., Chicago, IL). Descriptive statistics in case of normal distribution will be presented as mean and standard deviation, while if non-normal; median and 25th and 75th percentile will be used. Intergroup comparison will be done using t-test or Mann-Whitney test while Intra-group comparison will be done using student's t- test.

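### The within-group test is given only as Student's t-test: the paired form is not specified and there is no rank alternative for a 0–4 grade; within-arm results should be labelled descriptive

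*Combined protocol and SAP*

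**What the plan says.** Section 20 is the whole analysis plan. One sentence covers comparisons between arms and within an arm: "Intergroup comparison will be done using t-test or Mann-Whitney test while Intra-group comparison will be done using" Student's t-test. The word paired does not appear, and neither a signed-rank test nor a method for three visits is named. The only condition on normality concerns how data are summarised: "Descriptive statistics in case of normal distribution will be presented as mean and standard deviation, while if non-normal", medians and quartiles are given instead.

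Three other places describe the data that this test would meet.

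- **Repeated visits.** Section 11 recalls the same patients weekly for 14 days. The Quality of life text says participants will "complete the PROMS questionnaire thrice; baseline, after the first week, and at the end of the study after the second week".
- **Scale.** The Clinical parameters text says of the WHO scale: "It is graded from 0 to 4". The PICO table labels the primary outcome ordinal. The table in section 12 labels the same outcome a numerical rating score.
- **Entry.** The inclusion criteria require a WHO score of "Grade II, III and IV", so patients are selected on the scale that later measures their improvement.

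**The concern.** There are two separate issues.

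The first is specification. Baseline, week-1 and week-2 values from one patient are correlated, so the natural within-arm analysis works on each patient's differences. Student's t-test is a name for both the paired and the independent-samples form, and the two can give very different answers on the same data. The plan lets an analyst choose after seeing the data. It also accepts a rank test for the graded outcome between arms and not within arms, without giving a reason.

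The second is interpretation. Patients enter because their grade is at least II. Some will have been at a temporary high and will score lower next time with no drug effect. Natural healing, where it occurs, pushes the same way. Section 20 lists the two kinds of comparison side by side. It does not say which carries the efficacy conclusion, at which visit, or with what baseline adjustment. A report that one arm improved significantly and the other did not could then be taken as a difference between treatments.

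**Working it through.** **Inputs from the documents.** Effect size 1.011, power 80%, alpha 5%, 1:1 allocation, 17 per group (section 14). The group size is 33 in sections 11 and 13, and 21 in the application form. The documents give no between-visit correlation, no within-arm change and no distribution of WHO grades. Those are assumptions below.

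**Step 1: the plan's own figure.** Assuming a two-sided test, the normal approximation is n = 2(1.960 + 0.842)² / 1.011² = 15.4, rounded up to 16 per group. The two-sample t calculation gives 16.38, rounded up to 17, with 81.5% power at 17. The stated 17 therefore reproduces, and it is sized on the between-arm comparison. Nothing below changes it.

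**Step 2: standard errors.** Let the SD be σ at both visits and the correlation ρ.

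- Paired: SE = σ√(2(1 − ρ)/n)
- Unpaired: SE = σ√(2/n)
- Ratio, unpaired to paired: 1/√(1 − ρ), which is 1.20, 1.41 and 1.83 at ρ = 0.3, 0.5 and 0.7

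With positive correlation the unpaired standard error is too large, so the test rejects too seldom.

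**Step 3: size and power.** For a within-arm change of 0.5 SD, the paired effect size is 0.5/√(2(1 − ρ)), which equals 0.5 at ρ = 0.5. Simulation with normal data, nominal two-sided 5%:

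| n per arm | ρ | Unpaired: actual size | Unpaired: power | Paired: power |
|---|---|---|---|---|
| 17 | 0.3 | 2.1% | 26% | 37% |
| 17 | 0.5 | 0.8% | 23% | 49% |
| 17 | 0.7 | 0.1% | 19% | 71% |
| 33 | 0.3 | 2.0% | 52% | 65% |
| 33 | 0.5 | 0.7% | 52% | 79.5% |
| 33 | 0.7 | 0.1% | 53% | 95% |

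The paired test holds its size at about 5% throughout.

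**Step 4: how much improvement could selection alone produce?** Take a latent normal severity, rounded to grades 0–4, with entry at grade 2 or above, no drug effect and no healing. Let the latent mean run from 1.5 to 2.5, the SD from 0.8 to 1.0 and the correlation from 0.5 to 0.9. The mean change is then between −0.04 and −0.46 grade. A paired within-arm t-test is significant in 6% to 47% of arms at n = 17, and in 6% to 77% at n = 33. The direction is clear; the size is not determined by anything in the documents.

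**Step 5: does the between-arm comparison suffer in the same way?** No. Randomisation selects both arms alike, so the shift cancels. In a simpler model (continuous severity, entry above the median, n = 33, correlations 0.5, 0.7 and 0.8), comparing change between two identical arms rejected in 5.0%, 4.7% and 5.2% of trials.

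**The case against.** The strongest reply has three parts.

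**The text does not say unpaired.** A reader might infer that the plan ignores the pairing of visits. The documents do not support that: Student's t-test also covers the paired form, and the sentence can be read either way. This part of the reply stands. The claim has to be that pairing is not specified, and the unpaired figures in the working are conditional on one reading.

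**Regression to the mean is not a fault of this test.** It limits every within-arm test, including the paired and signed-rank tests recommended here. The standard remedy is a randomised concurrent control, and sections 8, 16a and 20 provide one. The aim in section 7 is comparative, and the sample size is built on a two-sample test. A reader might infer that the trial will conclude efficacy from within-arm p-values, or that its false-positive rate is inflated. No section says the first. The second does not follow, because the between-arm comparison is protected and an unpaired within-arm test would be conservative. This part stands too.

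**The scale is itself unsettled.** Section 12 calls the primary outcome a numerical rating score, which might be thought to justify a t-test alone. This carries little weight. The scale has five levels whatever its label, and the plan already admits a rank test for it between arms.

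What survives is the missing specification, the missing rank alternative, and the absence of any statement that within-arm results are secondary to the randomised comparison.

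**Conclusion.** The point holds as a cheap improvement, not as a flaw in the randomised comparison. Section 20 leaves the within-arm test open between two forms and gives no rank option for a 0–4 grade.

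If the unpaired form were used, the cost would be power. At an assumed correlation of 0.5 and a change of 0.5 SD, 79.5% falls to about 52% with 33 per arm, and 49% falls to 23% with 17. The loss is smaller at correlation 0.3 and larger at 0.7. If the analyst intends the paired form, this loss does not arise, and only the wording and the rank alternative need attention.

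Within-arm improvement is not evidence of efficacy in a trial that selects on a raised baseline grade. How far it could mislead cannot be stated more closely than the wide range in step 4, which rests entirely on assumed grade distributions and correlations.

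**What to change.** Replace the intra-group sentence in section 20 with text to this effect:

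> Change from baseline within each arm will be summarised at week 1 and week 2, using the paired t-test for PROMS and the Wilcoxon signed-rank test for the WHO and OMAS scores. These results are descriptive, and no efficacy conclusion will rest on them.

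Then add:

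> The efficacy conclusion will rest on one between-arm comparison of the week-2 WHO grade, adjusted for the baseline grade, using a proportional-odds (ordinal logistic) model with baseline grade as covariate. PROMS at week 2 will be compared between arms by ANCOVA with baseline PROMS as covariate.

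Section 12 should also use the same label for the WHO outcome as the PICO table.

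The cost is a few sentences. The baseline WHO grade is already needed for eligibility and PROMS is already collected at baseline, so there are no new data. The sample-size calculation is unaffected. The one real downside is that within-arm p-values can no longer be offered as evidence of efficacy.

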**D) Data monitoring:**

**21. Monitoring**

The collected data will be monitored by the main supervisor and co-supervisor. The entire study will be monitored by the Faculty of Dentistry's Ethical committee.

**22. Harms**

Any adverse effect from the treatment will be recorded and documented in details.

**23. Audit**

Auditing will be done by the Faculty of Dentistry's Ethical committee.

### **III. Ethics and dissemination**

#### **21. Research ethics approval**

After proper study design revision, the study protocol will be presented to the ethical committee for approval.

#### **22. Protocol amendments**

The protocol will be registered on clinicaltrials.gov in its current form, further amendments will be updated on the system.

#### **23. Informed consent**

informed consent will be obtained by the investigator from all study participants.

#### **24. Confidentiality**

The candidate will be responsible for data collection and storage. Patient's personal information will be available to the candidate and the research team only.

#### **25. Declaration of interest**

If there will be any conflict of interest it will be declared by the investigators.

#### **26. Access to data**

The Data (Demographic, Clinical and Analytical) will be available only to the supervisors

#### **30. post-trial care**

Any harm from the study, the participants will be managed completely.

### Application Form

#### Human Subjects

##### Kindly fulfill the following:

##### **Research title:**

Clinical Evaluation of MEBO Versus ~~Benzydamine~~ Hydrochloride In Management of Patients with radiotherapy induced Oral Mucositis: Randomized Clinical Trial

##### **Research objective:**

To assess the effect of MEBO versus ~~Benzydamine~~ Hydrochloride spray regarding clinical improvement of oral mucositis and quality of life of patients receiving ~~radiotherapy~~

##### **• Research Procedure in brief:**

A random sample of adult patients receiving radiotherapy or chemotherapy and having sign and symptoms of oral mucositis and this. Enrolled patients will be divided randomly into two groups, each consists of 21patients.

**Intervention group:** Patients will receive MEBO three times daily for two week

**Control Group:** Patients will receive ~~Benzydamine~~ Hydrochloride spray three times daily

**Follow up:** The patients will be recalled at one week interval for two week

as there is no treatment of oral mucositis available in Egyptian market

We will offer palliative treatment that will alleviate the pain of oral mucositis

##### **value and social benefits:**

treatment of chemotherapy and radiotherapy induced oral mucositis

